OLINK proteomic platform will be used to assess for biomarkers in blood. This platform is able to evaluate ~200 analytes, including all the inflammatory markers that are analyzed in skin, as well as cardiovascular markers, and neuro-immunological markers, including IL-13 and all the above Th2 chemokines, IFN gamma and the Th1 chemokines, as well as IL-17A, IL-22, PDE-related markers, and many other markers. Blood assessments will be performed on serum obtained at baseline, and Weeks 12, 24, 36, and 48.

A complete list of the biomarkers we will assess via OLINK can be found at:

<http://www.olink.com/proseek-multiplex/complete-biomarker-list/>

INCLUSION CRITERIA:

- 1) Male or female subjects who are at least 18 years old at the time of informed consent.
- 2) Subject is able to understand and voluntarily sign an informed consent document prior to participation in any study assessments or procedures.

- 3) Subject is able to adhere to the study visit schedule and other protocol requirements.
- 4) Females of childbearing potential (FCBP) must have a negative pregnancy test at Screening and Baseline. While on investigational product and for at least 28 days after taking the last dose of investigational product (IP), FCBP who engage in activity in which conception is possible must use one of the approved contraceptive options described below:
 - a. **Option 1:** Any one of the following highly effective methods: hormonal contraception (oral, injection, implant, transdermal patch, vaginal ring); intrauterine device (IUD); tubal ligation; or partner's vasectomy;

OR

 - b. **Option 2:** Male or female condom (latex condom or non-latex condom NOT made out of natural [animal] membrane [for example, polyurethane]); PLUS one additional barrier method: (a) diaphragm with spermicide; (b) cervical cap with spermicide; or (c) contraceptive sponge with spermicide.
- 5) If subject is a female of non-childbearing potential, she must have documented history of infertility, be in a menopausal state for one year, or had a hysterectomy, bilateral tubal ligation, or bilateral oophorectomy.
- 6) Subject has a history of at least 6 months of moderate to severe AA ($\geq 30\%$ scalp involvement) as measured using the SALT score; OR subject has $\geq 95\%$ loss of scalp hair for enrollment as AA totalis (AT) or universalis (AU) subtypes.
 - a. AT/AU will be limited to no more than 50% of the total subjects enrolled.

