Subjects are numbered sequentially. Each subject will be assigned a unique number and will keep this number for the duration of the study. Subject numbers will not be reassigned or reused for any reason. Subjects who discontinue or withdraw from the study before receiving a treatment assignment code, who re-enroll at a later time must be assigned a new subject number. Subjects should be identified only by their assigned identified code number. The investigator must maintain a subject master log linking the subject number to the subject's name. The investigator must follow all applicable privacy laws in order to protect a subject's privacy and confidentiality.

Randomization and Blinding

A subject who meets all of the inclusion and exclusion criteria will be assigned a randomization number pre-dose on day 0/baseline. The randomization number is distinct from the subject number.

After fulfilling the enrollment criteria, the subjects enrolled will be randomized in a 2:1 ratio of dupilumab to placebo.

The randomization for both sites will be performed by the designated Research Pharmacist/personnel at the Icahn School of Medicine utilizing the Web site <http://www.randomization.com> (or similar). The method uses random block sizes and randomly permuted blocks.

Approximately 60 subjects will be enrolled in the study in order to have at least 54 subjects complete (taking into account a 10% drop out rate). Subjects will be assigned a randomization number on day 0/Baseline. The randomization schema will be kept confidentially after generation.

INVESTIGATIONAL DRUG SUPPLY AND BLINDING:

Regeneron Pharmaceuticals will provide dupilumab 300 mg for 40 subjects in Phase I and for all 60 subjects during Phase II (a total of 25 doses in Phase I to those 40 subjects randomized to receive dupilumab, followed by another 24 doses in Phase II; a total of 24 doses in Phase II to the 20 subjects who received placebo in Phase I).

Eligible patients will receive a 600 mg SC dupilumab loading dose (300 mg initial dose, followed by a 300 mg loading dose) on day 0/Baseline, and then continue with 300 mg SC dupilumab once weekly starting on day 8. At Week 24, subjects previously on dupilumab will receive 1 injection of 300 mg dupilumab and 1 injection of placebo to maintain the blind of the study; subjects previously on placebo will receive 2 injections of 300 mg dupilumab. All subjects should be observed for 30 minutes following the injections at Baseline and at Week 24.

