Matching placebo prefilled syringes (that will appear identical to the dupilumab syringes) will be provided by the company to the study sites. The subjects and the staff will remain unaware of the individual treatment assignment during the study. All study medication will be stored in a secure cool area between 2-8°C. Study drug will be administered to subjects at each study visit, with subsequent weekly injections performed by the patients at home. Patients (and/or caregivers) who are willing and able to administer dupilumab outside of the clinic will be trained on injecting study drug during the initial clinic visit.

We will query the subjects during each study visit on any missed injections and document this information. The investigative sites will account for all study drug dispensed and stored during the study.

STATISTICAL CONSIDERATIONS:

Sample Size Calculation

The primary outcome for this study is the SALT change at week 24. For patients with similar disease severity, a change in SALT of less than 5 units was observed ([name] et al, 2019). Assuming that dupilumab will induce a change in SALT of at least 25 units with a standard deviation of 10 at week 24, a sample size of 54 completed patients randomized 2:1 treatment to placebo (i.e. 36 in the treatment arm, 18 in the placebo arm) will provide 97% power to detect differences with Placebo based on a two-sided Student's t-test with a 0.05 type I error. Assuming that 10% of patients drop out of the study, we plan to enroll 60 total patients (i.e. 36 in the treatment arm, 18 in the placebo arm).

Demographics and Other Baseline Characteristics

Descriptive statistics of demographics and other baseline characteristics will be presented for all subjects and tabulated by treatment group. Presentations of age, sex, ethnicity, race and baseline will also be given. Other baseline characteristics include height, weight, and vital signs, duration of the AA and AD, concurrent diagnoses from medical history and indications for concomitant medication, concomitant medication, and previous AA and AD treatments.

Analysis of Primary Endpoint

A Mixed effect Model Repeated Measurement (MMRM) will be used to detect any overall differences in the treatment effect at week 24 compared to baseline.

Analysis of Secondary Endpoints

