by our group. To define cellular and molecular biomarkers of AA in skin biopsies, biomarkers will be divided into those that show significant group differences and those that do not. Multiple regression models will be used to determine the best set of biomarkers that predict disease activity and response.

Gene expression changes in hair keratins and the immune axes (Th1, Th2, Th17, Th22) will be jointly correlated with clinical responses by multivariate analysis using multivariate u-statistics and R package muStat, as previously reported [43].

Data Transfer and Management

Data including the patient info, demographics, clinical scores and treatment allocation code will be sent to our Biostatistical Team in password-protected files.

Data from the [name] Lab (where all mechanistic blood and skin studies will be done), including FASTQ files, real-time PCR (RT-PCR), and serum proteomics will be deposited in the Mount Sinai Box and Amazon S3 bucket, having the necessary safeguards for protection of human subjects research. [name] lab members will not have access to the treatment code until all lab work has been completed and the data transferred to our Biostatistical Team.

All data management steps taken to reformat and merge the clinical and laboratory data will be carried out using R codes, so all the steps of the processes can be reproduced.

Management of the Analysis

Analysis of RT-PCR and RNA-sequencing will all be conducted using R language and bioconductor packages. Codes will be QC-ed by at least one independent member of the Biostatistical Team, other than the member who coded the analysis.

Analysis will be run in our desktops, with a backed up copy in the Mount Sinai Box. Analysis results will be shared with the study teams of Drs. [name], [name], and [name], as well as [name] who holds joint appointments at Rockefeller University and Mount Sinai, and [name] who is our study consultant, via the Mount Sinai Box. Once the analysis is finalized, all data will be deposited in [name] and [name] central file storage system (CFS), which is accessible to all research members. Both Mount Sinai Box and the CFS have backup capabilities and are encrypted and password protected. Access to the Mount Sinai Box specific for the project will be shared with the Rockefeller team and [name].

Analysis of Safety and Tolerability

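### No shrinkage, predictor limit or validation is stated for the best-set biomarker regression, so its apparent fit would be optimistic

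*Combined protocol and SAP*

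**What the plan says.** The steps are in *Statistical Considerations*, under *Analysis of Mechanistic Endpoints*. Expression in lesional and non-lesional skin, from RT-PCR and RNA-sequencing, is compared by mixed models. The p-values of the moderated and paired t-tests are adjusted by Benjamini-Hochberg, with no false discovery rate given. For skin-biopsy markers the plan then says that "biomarkers will be divided into those that show significant group differences and those that do not". It does not say which groups are meant (lesional against non-lesional, or drug against placebo), or whether significance here is after adjustment. The next sentence is the modelling step: "Multiple regression models will be used to determine the best set of biomarkers that predict disease activity and response".

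The skin candidates are the markers named in *Mechanistic Analyses*, about 47 by my count, plus the RNA-sequencing transcriptome. The serum panel is described separately under *Blood Analyses*: "This platform is able to evaluate ~200 analytes". The sample size paragraph gives the completers as "36 in the treatment arm, 18 in the placebo arm".

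The text available to me names no selection algorithm, shrinkage, cap on predictors, adjustment for arm, cross-validation, hold-out set or external validation for this regression. The mechanistic endpoints are labelled exploratory, but finding response biomarkers is a declared purpose of the mechanistic work.

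**The concern.** Choosing predictors and judging their fit on the same few dozen patients makes the fit look better than it is. The screen does not remove the problem, because it asks a different question from the regression. A marker can differ between lesional and non-lesional skin, or move on drug, and still say nothing about which patient regrows hair.

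The protocol expects many markers of that kind. Its background reports strong lesional up-regulation of Th1, Th2 and IL-23 products and loss of hair keratins, and the skin panel is based on such findings. Those markers should pass a group screen, and pass it correctly. The search against response then starts from a well-filled list with no stated protection. At stake is a response signature that fits this trial, fails in new patients, and may be carried into the design of the next study.

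**Working it through.** **Inputs from the documents:** 54 completers, 10% dropout, 36 against 18, about 47 named skin markers.

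**Assumptions:** independent normal markers; false discovery rate 0.05; 20,000 genes where the transcriptome is considered; forward selection with entry at p<0.05 and at most five predictors.

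**1. The plan's own figure.** 54 / (1 − 0.10) = 60, as stated. That number is set for the SALT comparison. No sample size is given for the biomarker model, so n is 36 + 18 = 54 with arms pooled, or 36 on dupilumab alone.

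**2. The screen under pure noise.** Markers were simulated with no relation to group or response and screened 36 against 18.
- With Benjamini-Hochberg, at least one marker passes in about 5% of runs, whether there are 47, 200 or 20,000 markers. A significant regression follows in under 0.5%.
- Unadjusted at p<0.05, at least one marker passes in 92% of runs (47 markers) or 100% (200 or 20,000). The overall F test for response is still significant in only 4–5%, because the screen was on group.

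**3. The search after the screen.** Let m markers pass for real group reasons, with none related to response. Forward selection starts if the smallest of m independent p-values is below 0.05, so P(false signature) = 1 − 0.95^m. Results at n=54:

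| m | 1 − 0.95^m | Simulated | Apparent R² when a model is found | R² in new patients |
|---|---|---|---|---|
| 5 | 0.226 | 21.9% | 0.11 | −0.14 |
| 10 | 0.401 | 40.2% | 0.13 | −0.16 |
| 20 | 0.642 | 64.8% | 0.16 | −0.20 |
| 47 | 0.910 | 91.1% | 0.27 | −0.35 |

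Repeat simulations gave 40–43%, 63–65% and 90–92% for m = 10, 20 and 47. With inter-marker correlation 0.3 the rates fall to 35%, 56% and 80%. The formula does not contain n, so 36 patients give much the same rates (39%, 62%, 91%), with worse R² in new patients (−0.25, −0.32, −0.57).

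**4. If all m markers are kept instead.** Expected apparent R² under noise is m / (n − 1): 10/53 = 0.19, 20/53 = 0.38, 47/53 = 0.89 (simulated 0.19, 0.37, 0.88). The F test keeps its error rate near 5%, so here the optimism lies in R² and not in the test.

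**5. Pooling arms.** The sample size paragraph assumes "a change in SALT of at least 25 units with a standard deviation of 10 at week 24", against under 5 units without active treatment, so a difference of up to about 25 − 5 = 20. I assumed five markers shifted by drug by 0.8 to 1.5 SD, a SALT difference of 10 to 20, and no link within arm. The pooled regression is significant in 28% to 99% of runs. With arm in the model it is 4–6%.

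**6. Does validation catch it?** With n=54, pure noise, a screen on response and at most five markers kept, repeating the selection inside 5-fold cross-validation gives mean R² of −0.21 (47 markers) and −0.37 (200). Leaving selection outside the folds gives a false +0.13 and +0.28. Elastic net itself was not simulated.

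**The case against.** A reader might infer that the plan would produce a signature from pure noise almost every time. That result does arise if 200 noise markers are screened against the response at unadjusted p<0.05: apparent R² is then about 0.56 at n=54 and 0.69 at n=36. The documents do not describe that procedure. The stated screen is on group differences, the same section describes Benjamini-Hochberg adjustment, and the screening step concerns skin biopsies while the roughly 200 analytes are a serum panel. With 200 markers and an unadjusted group screen, apparent R² is about 0.16 to 0.19 at n=54, and the F test is significant in only 4–5% of runs. This objection stands and limits the point to the second step.

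It is also fair that the plan does not specify ordinary least squares and promises no performance figure. This is under-specification, not a wrong method chosen, so the rates in step 3 depend on a selection rule that I had to assume. The plan does, however, commit to choosing a best set by regression, and nothing in it guards that choice.

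Finally, the endpoints are exploratory and no treatment decision in the trial depends on them. That lowers the severity but does not make an uncorrected fit right. Two other provisions do not fill the gap: the multivariate u-statistic analysis is a separate correlation step, and the independent code check finds coding errors, not optimism.

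**Conclusion.** The point holds in limited form. Benjamini-Hochberg adjustment would stop most pure noise at the screen, if it governs the screen. It does not protect the search that follows among markers with real group differences and no link to response. There a false signature appears in about 40%, 64% and 91% of runs with 10, 20 and 47 such markers at n=54, with negative R² in new patients.

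These rates assume independent markers and forward selection at p<0.05 with at most five predictors. Correlation between markers lowers them, and a different selection rule would change them. That the apparent fit is optimistic does not depend on that rule, as step 4 shows. The pages between the preliminary data and the secondary endpoint list were not available to me, so the absence of validation is claimed only for the rest.

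The primary and secondary analyses are unaffected. I rate this a cheap improvement of low severity.

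**What to change.** Replace the best-set regression with a short specification, fixed before the lab data are merged with the treatment code:

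- Define the groups compared in the screen, the false discovery rate, the candidate list and the outcome to be predicted.
- Fit a penalised regression, for example elastic net, with treatment arm in the model.
- Put all screening, selection and tuning inside cross-validation. Step 6 shows that leaving selection outside the folds keeps much of the false fit.
- Report cross-validated (or bootstrap optimism-corrected) performance and how often each marker is selected, in place of apparent fit.
- Label the resulting set hypothesis-generating.

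The cost is a paragraph of text and some extra R code on data already being collected. The reported performance will look less favourable.

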 - ⁹ For AD pts, one biopsy of lesional skin close to the biopsy performed at baseline. If no biopsy was performed at baseline, then no biopsy required at this visit (regardless of active lesions);
 - ¹⁰ Optional biopsy of lesional scalp and lesional AD skin (if applicable);
 - ¹¹ Initial dose will be a loading dose of 600mg (two injections of 300 mg dupilumab or placebo), followed by a required 30 minute observation period;
 - ¹² Subjects previously on dupilumab will receive 1 injection of 300 mg dupilumab and 1 injection of placebo to maintain the blind of the study; subjects previously on placebo will receive 2 injections of 300 mg dupilumab. Both groups will be observed for 30 minutes following the injections.
 - ¹³ For subjects with active AD lesions at Screening and/or Baseline, these assessments should be done at each visit.
- * Performed only if Early Termination visit occurs prior to Week 24.

Appendix 1. Clinical Assessments/Scoring

Alopecia Areata Assessments:

Severity of Alopecia Tool (SALT)

Scalp divided into four areas: vertex (40% of scalp surface area), right profile (18% of scalp surface area), left profile (18% of scalp surface area), and posterior scalp (24% of scalp surface area). Percentage of hair loss in these areas is multiplied by percent surface area of the scalp in that area. SALT score is the sum of percentage of hair loss in all areas.

SALT score:

	Left Side (18%)	Right Side (18%)	Top (40%)	Back (24%)	
Percentage Hair Loss					
Percentage X Area	X 0.18	X 0.18	X 0.4	X 0.24	
Total	+	+	+	=	

Eyelash/Eyebrow Assessment Score

0= None

1= Minimal eyelashes/eyebrows

2= Moderate eyelashes/eyebrows

3= Prominent eyelashes/eyebrows

4= Very prominent eyelashes/eyebrows

Alopecia Areata Physician's Global Assessment (aaPGA):

The aaPGA is used to assess the clinical response to treatment based on a 6-point scale ranging from 0 (no regrowth) to 5 (100% regrowth):

No regrowth	<25% regrowth	25-49% regrowth	50-74% regrowth	75-99% regrowth	100% regrowth
0	1	2	3	4	5

Atopic Dermatitis Assessments:

Scoring atopic dermatitis (SCORAD)

3 components: A) % body surface area involvement (the rule of 9's); B) Intensity of eczema evaluated on representative lesions, rating 5 lesions (scale 0 to 3) for features including erythema, thickness, excoriations, wound/scab formation, lichenification, and xerosis; C) Functional impact based on pruritus (0 to 10) and sleep disturbance (0 to 10). Final score determined by $SCORAD = A/5 + (7 \times B/2) + C$

SCORAD INDEX
[RULE OF 9'S]

ANTERIOR INFANT POSTERIOR

A: EXTENT Please indicate the area involved 	A/5 + 7B/2 + C 
B: INTENSITY 	
C: SUBJECTIVE SYMPTOMS PRURITUS + SLEEP LOSS 	

CRITERIA	INTENSITY
Erythema	
Oedema/Papulation	
Oozing/crust	
Excoriation	
Lichenification	
Dryness*	

* Dryness is evaluated on uninvolved areas

MEANS OF CALCULATION
INTENSITY ITEMS (average representative area)
0 = absence
1 = mild
2 = moderate
3 = severe

VAS

Init: _____ ID # _____

Date: _____

Subject VAS:

Draw a vertical line across the present line to represent the average for the last 3 days or nights regarding how much itching and sleep loss you have experienced:

Itching:

Sleep Loss:

Eczema Area and Severity Index (EASI)

The EASI is used to assess the severity and extent of AD. Four AD disease characteristics will be assessed (0 = absent to 3 = severe). Area of AD involvement will be assessed as a percentage by involved body area of the head, trunk, arms, and legs, and converted to a score of 0 to 6.

EASI	Head & Neck	Upper Extremities	Trunk, Axillae and Genitals	Lower Extremities & Buttocks
Erythema				
Infiltration / Papulation				
Excoriation				
Lichenification				
Sum				
Area Score				
Sum x Area Score				
x	X .1	X .2	X .3	X .4
Total				
Area Score (of the respective body region): 0=No Eruption 1=< 10%, 2= 10%-29%; 3=30%-49%, 4 = 50% - 69%; 5= 70% - 89%, 6= 90% - 100%				
Erythema	0 - None 1 - Mild Faintly detectable erythema; very light pink 2 - Moderate Dull red, clearly distinguishable 3 - Severe Deep / dark red			
Infiltration / Papulation	0 - None 1 - Mild Barely perceptible elevation 2 - Moderate Clearly perceptible elevation but not extensive 3 - Severe Marked and extensive elevation			
Excoriations	0 - None 1 - Mild Scant evidence of excoriations with no signs of deeper skin damage (erosion,crust) 2 - Moderate Several linear marks of skin with some showing evidence of deeper skin injury (erosion,crust) 3 - Severe Many erosive or crusty lesions			
Lichenification	0-None 1 - Mild Slight thickening of the skin discernible only by touch and with skin markings minimally exaggerated 2 - Moderate Definite thickening of the skin with skin markings exaggerated so that they form a visible criss-cross pattern 3 - Severe Thickened indurated skin with skin markings visibly portraying an exaggerated criss-cross pattern			

IGA (Investigator's Global Assessment)

IGA Severity	Features
4 – Severe Disease	Severe erythema and severe papulation/infiltration
3 – Moderate Disease	Moderate erythema and moderate papulation/infiltration
2 – Mild Disease	Mild erythema and mild papulation/infiltration
1 - Almost Clear	Just perceptible erythema and just perceptible papulation/infiltration
0 - Clear	No inflammatory signs of AD

Appendix 2. Subject Questionnaires (AASIS and AA-QLI)

ID# _____

Alopecia Areata Symptom Impact Scale (AASIS)

Alopecia areata is a condition that may affect you. Please rate how severe the following symptoms of your alopecia areata have been *in the past week*. Please select one response from 0 (symptom has not been present) to 10 (the symptom was as bad as you can imagine it could be) for each item.

	Not Present	As bad as you can imagine
Scalp hair loss	0 	10 
Body or eye lashes hair loss	0 	10 
Tingling/numbness of the scalp	0 	10 
Itchy or painful skin	0 	10 
Irritated skin	0 	10 
Feeling anxious or worry	0 	10 
Feeling sad	0 	10 

Your alopecia areata may interfere with your daily functioning. Please rate how the following items were interfered with by alopecia areata *in the past week*: Please select one response from 0 (did not interfere) to 10 (interfered completely) for each item.

	Did not Interfere	Interfered completely
Work	0 	10 
Enjoyment of life	0 	10 
Interaction with others	0 	10 
Daily activities	0 	10 
Sexual relationships	0 	10 
Quality of life	0 	10 

Alopecia Areata Quality of Life Index (AA-QLI)

Subjective symptoms			
1.	I feel uncomfortable using a wig	Very much A lot A little Not at all	   
2.	I tend to hide my scalp with hats or bandages	Very much A lot A little Not at all	   
3.	I am sad about the appearance of my hair/eyebrows/eyelashes	Very much A lot A little Not at all	   
4.	I worry about having this hair problem for the rest of my life	Very much A lot A little Not at all	   
5.	I cannot forget that I have this hair problem	Very much A lot A little Not at all	   
6.	I worry that it might spread	Very much A lot A little Not at all	   
7.	I do not take my wig/hat/bandana off in front of my partner/relatives/ friends	Very much A lot A little Not at all	   
8.	It costs me a lot of money to look after my hair	Very much A lot A little Not at all	   
9.	I am afraid my children may have alopecia areata	Very much A lot A little Not at all	   
Relationship			
10.	I feel that people find it unpleasant to look at me	Very much A lot A little Not at all	   
11.	I think that other people notice my hair/eyebrows/eyelashes problem	Very much A lot A little Not at all	   

12.	I am afraid that other people think my hair looks badly cared for	Very much A lot A little Not at all	   
13.	I am embarrassed when going out to a party	Very much A lot A little Not at all	   
14.	I have to explain to others what is wrong with my hair/eyebrows/eyelashes	Very much A lot A little Not at all	   
15.	I feel that others are afraid of catching diseases from me	Very much A lot A little Not at all	   
16.	I feel I have sexual difficulties because of alopecia areata	Very much A lot A little Not at all	   
17.	I feel I have difficulties in establishing relationships with friends and/or relatives	Very much A lot A little Not at all	   
18.	My work/studying has deteriorated because of alopecia areata	Very much A lot A little Not at all	   
Objective signs			
19.	My scalp is visible	Very much A lot A little Not at all	   
20.	I lose tufts of hair when I comb or shampoo	Very much A lot A little Not at all	   
21.	I feel itchy on my scalp	Very much A lot A little Not at all	   

Amendment #1 Description

Page 1 – Amendment # 1 January 31, 2018 added

Page 2 – Table of Contents added

Page 7, 3rd paragraph – EG changed to [name] and sentence clarified.

Page 10, last paragraph (Study Design Overview) – Added “The study will take place at two sites: Icahn School of Medicine at Mount Sinai, and Rockefeller University.” Also “(20 out of 60 subjects)” was added for clarification of the number of subjects allowed to have AA and AD.

Page 11, 1st paragraph – Added “(30 out of 60 subjects)” to clarify number of subjects allowed to have AT or AU.
Added “Once the required number of subjects in each of these sub-categories is met, additional subjects in those categories will not be enrolled” for clarification.

Page 11, 4th and 5th paragraph – Description regarding clinical assessments was split into two types to distinguish between those for all subjects (AA) and those for the subset of subjects with AA + AD: “clinical assessments (SALT, and eyebrow/eyelash assessment score), and additional skin assessments if he/she concurrently has atopic dermatitis (EASI, IGA, SCORAD)”.

Page 12, 1st paragraph – Size of biopsy was corrected to 4.5 mm (which matches consent form).

Page 12, 2nd and 3rd paragraph – sections clarified regarding the loading dose and all other doses.

Page 12, 5th paragraph (Independent Expert Assessment) - [name] will not approve screening photos as both PIs are experts in diagnosing AA, thus that statement has been deleted. [name] will still review photographs of those subjects that consent to them, to assess improvement/progress during the study.

Pages 17-21 - Description regarding clinical assessments was split into two types to distinguish between those for all subjects (AA) and those for the subset of subjects with AA + AD: “clinical assessments (SALT, and eyebrow/eyelash assessment score), and additional skin assessments if he/she concurrently has atopic dermatitis (EASI, IGA, SCORAD)”.

Page 17 – Standardized Clinical Photography deleted from Screening visit and added to Baseline visit.

Page 19 Visit 8 – Added for clarification regarding Week 24 injections “(subjects

previously on dupilumab will receive 1 injection of 300 mg dupilumab and 1 injection of placebo to maintain the blind of the study; subjects previously on placebo will receive 2 injections of 300 mg dupilumab). All subjects should be dupilumab). All subjects should be observed for 30 minutes following the injection to preserve the blind.

Page 21 – Added section:

LABORATORY TESTING:

Each site may utilize their own local lab for CBC, CMP, LDH, CRP, IgE, HIV, HBV, HCV, Quantiferon Gold, and pregnancy testing. Lab certifications for any lab used should be kept in the study binder. RU will have to transport biopsy samples as well as blood samples for mechanistic testing (and potentially IgE testing) to Mount Sinai via proper and documented means.

Page 22 – (Study Withdrawal) - Description regarding clinical assessments was split into two types to distinguish between those for all subjects (AA) and those for the subset of subjects with AA + AD: “clinical assessments (SALT, and eyebrow/eyelash assessment score), and additional skin assessments if he/she concurrently has atopic dermatitis (EASI, IGA, SCORAD)”.

Page 24 after first bullet – added “Duration of study drug suspension should be reviewed on a case by case basis and can be discussed among the PIs” in cases of temporary discontinuation of drug.

Page 25 Added (or similar) in reference to the website used to create the randomization code.

Page 26, 1st paragraph – added for clarification: “At Week 24, subjects previously on dupilumab will receive 1 injection of 300 mg dupilumab and 1 injection of placebo to maintain the blind of the study; subjects previously on placebo will receive 2 injections of 300 mg dupilumab. All subjects should be observed for 30 minutes following the injections at Baseline and at Week 24.”

Page 28, 2nd paragraph – Typo corrected as well as clarifications made, and statement added regarding the sharing of photos and results with [name].

Page 33 and 34 (Schedule of Events) – Clinical assessments split into multiple rows for clarification; corrections as to when specific procedures are done; and clarifications made to the footnotes.

Page 35-38 Additional calculation tables added to descriptive details regarding assessments.

Page 39-41 Added “Appendix # 2 Subject Questionnaires (AASIS and AA-QLI)

Page 42 – Added Amendment # 1 Description.

Amendment #2 Description

Page 24 Unblinding Section Paragraph 2 – “the data safety monitoring board” was deleted as there is no DSMB for this study. It had been originally included in error.

Amendment #3 Description

Page 1 – [name] was removed as a co-investigator and Protocol Version was added: January 08, 2020 Amendment # 3

Pages 9, 10 and 11 Endpoints - Statistician reviewed protocol and recommended some revisions to the endpoints. Primary endpoint was revised to only compare Week 24 to Baseline instead of comparing both Week 24 and 48 to Baseline as Week 24 ends the blinded placebo controlled phase. Three secondary endpoints evaluating lower improvements in SALT scores were deleted. Second mechanistic endpoint analyzing relapse was removed.

Page 27 and 28 Statistical Consideratons – The statistical analyses sections were updated to correlate with the updated Primary and Secondary Endpoints. The sections defining Analysis of Mechanistic and Exploratory Endpoints have been expanded upon and updated with the most recent information available to date.

Page 13 Study Design Overview – The option for subjects to seek other treatments (or obtain commercially available dupilumab) at Week 48 was added.

Page 17 – Concomitant Treatment - If subjects seek other treatments (or obtain commercially available dupilumab) at Week 48, then these treatments must be documented as concomitant medications.
